Data extraction for children in the immunization register will occur by using a sampling interval to ensure children are sampled throughout the entire year. The sampling interval will be created by taking the total number of children entered into the immunization register for the previous 12 months and dividing by our required sample size (N = 30). For instance, if 90 children were entered into the register in the past 12 months, the sampling interval will be 3; if only 30 children were entered into the register in the past 12 months, the sampling interval will be 1. With the sampling interval, the data collector will count backwards from the most recent entry in the immunization register and begin gathering data. The data collector will record the name, date of birth, and record the date(s) of immunization for each of the birth vaccines in the immunization register. Using the name and date of birth, the data collector will then cross-check with the maternity registers to confirm that same child's date of birth. Records that are missing either a date of immunization or date of birth will be recorded to help determine how many children were potentially born out of the facility, or have incomplete records, but will not count towards the total desired sample size for timeliness coverage. Data collectors will continue working backwards through the registers entering data for every Xth child (according to the sampling interval) until they have successfully recorded the

date of immunization and date of birth for 30 children. If they reach the end of the year without entering complete data on 30 children, the data collector will be instructed to loop back through the year but start now on the second child registered when counting.

At end line:

The end line registry extraction will utilize the same sampling technique as baseline. The same sample size (N = 30) will be used with the sampling period being the duration of the study period.

Proportion of babies born in facilities receiving birth dose vaccines within 24 hours – Maternity registry extraction

At baseline:

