The same sampling interval/methodology described above will be utilized again, only this time the data collectors will begin with the birth registers to determine their sampling interval. Then this interval will be used to pull names first from the birth register to select a sampling of babies that were born in that specific facility and then cross-checked with immunization dates for birth vaccines in the immunization registers. Records that are missing either a date of immunization or date of birth will be recorded to help determine how many children were not vaccinated at that facility or lack complete records. Data collectors will continue working backwards through the registers entering data for every Xth child (according to the sampling interval) until they have successfully recorded the date of birth and date(s) of immunization for 30 children.

At end line:

The end line registry extraction will utilize the same sampling technique as baseline. The same sample size (N = 30) will be used with the sampling period being the duration of the study period. As there will be children who may not receive their birth dose vaccines before the end line data collection, this indicator will focus on those children who did/did not receive the vaccine within 24 hours.

Contingency plan:

In the event of worsening COVID-19 transmission, facility staff will locate the relevant registry pages and will send photo records of the pages to study staff. Study staff will then continue with data extraction as outlined.

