2.14 Limitations

This pilot study will have several key limitations. The sample of the study will be small and purposeful in that it will only include 15 health facilities that meet a set of pre-defined criteria (see above). Therefore, this work will not be statistically precise nor be nationally representative and the participating sites will likely not experience certain challenges pertaining to birth vaccines that are undoubtedly experienced elsewhere in Cameroon as a whole (such as sites located in conflict zones, etc.). Instead, the purpose of the sample is to assess the feasibility of integration of birth dose vaccines BCG and OPV0 in maternity and newborn care services to gather lessons and formulate recommendations for the broader routine immunization and maternal and child health programs.

Data collected from registers to determine timing of vaccine administration results is a limitation in that it requires us to have both a date of birth and date of vaccination in facility registers. Therefore, babies who were born out of the facility (either at home or in a different facility) will not contribute to the aggregated figures, the same goes for babies who were born in the health facilities but receive vaccination elsewhere. Furthermore, we cannot guarantee the accuracy of the facility records. Key barriers and factors associated with the birth dose process will be descriptive in nature.

3 COVID-19 Impacts

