For sampling interval, count how many children are entered within a year of today's date. Divide this total number by 30 to get your sampling interval. For instance, if there are 300 children within the year, your sampling interval is 300/30 or 10. Therefore, you will enter every 10th child until you reach 30 children in total. For this work you will also be looking the child up in the immunization register. Please ask the in-charge and the EPI nurse to gather this information when it is not in use.

	Delivery register			Immunization register									
Child Name	Q1. Date of Birth	Q2. Date of OPV0 administered	Q3. Date BCG administered	Q4. Were you able to find this child based on name	Q5. Date of OPV0 administered	Q6. Date BCG administered							
	A - Date of birth listed? 1 = Yes, 2 = No (If no, skip Q1.B)	A – Was vaccine administered? 1 = Yes, 2 = No (If no, skip Q2.B)	A – Was vaccine administered? 1 = Yes, 2 = No (If no, skip Q3.B)	and birth date in the register? 1 = Yes, 2 – No (if no, skip Q5 and Q6)	A – Was vaccine administered? 1 = Yes, 2 = No (If no, skip Q5.B)	A – Was vaccine administered? 1 = Yes, 2 = No (If no, skip Q6.B)							
	B - Date listed C – Time of Birth	B - Date listed C – Time of vaccine administration	B - Date listed C – Time of vaccine administration		B - Date listed C – Time of vaccine administration	B - Date listed C – Time of vaccine administration							

Newborn data tool

This form should be used to record data about each delivery during the study period. Data should be completed by a delivery nurse and shortly after the baby is discharged.

Child #:	Facility		Date:	//
	Code:			

Delivery Inform	nation	OPV0→	
Gender	Male1 Female2	OPV0	Yes1 No2
Date of birth, Time of birth, and birth weight	/ : : (DD/MM HH:mm) Grams	DATE AND TIME THE BABY RECEIVED OPVO	/ : : (DD/MM hh:mm)
CIRCLE ALL SERVICES PROVIDED	EPI visitA Dr visitB PNCC OtherX If other, specify:	IF NO, PLEASE CIRCLE THE PRIMARY REASON	Caregiver refused1Stock out2Scheduled for later3EPI was not open4Left before receiving the vaccine6Too few children to open a vial7Not eligible for clinical reasons8Not enough time for vaccination9Other10If other, specify:
OXYTOCIN GIVEN?	Yes1 No2	BCG→	
DISCHARGE DATE AND TIME	/ :	BCG	Yes1 No2
PLEASE LIST ANY CC	MPLICATIONS OR COMMENTS ON THE BIRTH:	DATE AND TIME THE BABY RECEIVED BCG	/ ::
		IF NO, PLEASE CIRCLE THE PRIMARY REASON	Caregiver refused

Notes for touchpoint calls

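### The sampling rules for the primary proportion conflict: a both-dates quota at baseline, wording that keeps all births at end line and in the extraction tool, and three different end line windows

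*Combined protocol and SAP*

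**What the plan says.** Section 1.2 states objective 2 as a change among facility births, and Section 2.10 makes the change in the 24-hour proportion the primary outcome. Section 2.11 gives no denominator.

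- **Baseline (Section 2.9.1, maternity registry extraction).** Collectors sample the birth register, look each child up in the immunization register, and continue "until they have successfully recorded the date of birth and date(s) of immunization for 30 children". The method is said to be the one already described for the immunization-register sample. There, records lacking either date are noted "but will not count towards the total desired sample size for timeliness coverage". The maternity paragraph also has incomplete records noted, but does not repeat that clause.
- **End line (same section).** "The end line registry extraction will utilize the same sampling technique as baseline", "with the sampling period being the duration of the study period". The text then says that some children may still be waiting for their doses, so "this indicator will focus on those children who did/did not receive the vaccine within 24 hours".
- **Delivery register tool (Section 5.3).** Collectors are told to "count how many children are entered within a year of today's date". It continues: "Therefore, you will enter every 10th child until you reach 30 children in total". There is no both-dates condition, and one field records a child who cannot be found. The immunization register tool just before it does carry the condition.
- **Limitations (Section 2.14).** Using registers is a limitation because "it requires us to have both a date of birth and date of vaccination in facility registers". Babies born in the facility but vaccinated elsewhere do not contribute.
- **Study population (Section 2.4).** The periods named are a one-year baseline and the intervention period.

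**The concern.** A birth with no dose recorded at the facility is a birth that was not shown to be vaccinated on time, and objective 2 needs it in the denominator. A quota filled only by births with both dates leaves it out. The sample then estimates timeliness among births traced to a dose, which is higher than timeliness among all births.

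If the same exclusion applied at both rounds and the traced share were near 100%, little would be lost. But the end line wording and the tool can each be read as keeping untraced births. A collector cannot follow all three texts, and the analysis section does not settle which denominator is meant. The primary change can therefore be computed in several incompatible ways, with errors in opposite directions or almost none.

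The end line window raises a second problem of the same kind. The tool looks back one year, Section 2.9.1 uses the study period, and Section 2.4 refers to the intervention period. The first two bring pre-intervention births into the end line sample and pull the measured gain towards zero.

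**Working it through.** **Figures in the plan.** The 30 records per facility have no derivation to reproduce. The interval examples are correct: 90/30 = 3 and 30/30 = 1 (Section 2.9.1), and 300/30 = 10 (Section 5.3).

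**Notation.** p is the share of facility births vaccinated within 24 hours, and v is the share with both dates in the facility registers. Subscript 0 is baseline and 1 is end line. t is the traced share among births not vaccinated on time. Every timely birth is assumed traced.

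**Inputs.** p0 = 4% (BCG) and 7% (OPV0) are the 2019 results in Section 1.1, from 30 other sites with no denominator described. The documents do not give v0 or p1. I assume v0 = 80% or 90%, and p1 = 50%.

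**Formulas.**
- Target: p1 − p0.
- A both-dates sample estimates p/v. As a check, simulating the 30-complete-records quota with p = 7% and v = 60% (20,000 runs) averaged 11.6%, against 7/0.6 = 11.7%. The first 30 births averaged 7.0%.
- Only baseline restricted: p1 − p0/v0.
- Both rounds restricted: p1/v1 − p0/v0, with t0 = (v0 − p0)/(1 − p0) and v1 = p1 + (1 − p1)·t1. Stable tracing means t1 = t0.
- Tool's rule at both rounds: p1 − p0, with untraced births counted as not timely.

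**Example, BCG, v0 = 80%.** p0/v0 = 0.04/0.80 = 5.0%. Only baseline restricted: 50 − 5.0 = 45.0. For both rounds, t0 = 0.76/0.96 = 0.792, v1 = 0.5 + 0.5 × 0.792 = 0.896, and 0.5/0.896 = 55.8%, so the change reads 50.8.

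| Vaccine, v0 | True gain | Only baseline restricted | Error | Both restricted, stable tracing | Error |
|---|---|---|---|---|---|
| BCG, 80% | 46.0 | 45.0 | −1.0 | 50.8 | +4.8 |
| BCG, 90% | 46.0 | 45.6 | −0.4 | 48.3 | +2.3 |
| OPV0, 80% | 43.0 | 41.25 | −1.75 | 47.3 | +4.3 |
| OPV0, 90% | 43.0 | 42.2 | −0.8 | 45.1 | +2.1 |

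**If tracing changes between rounds.** With both rounds restricted, the overstatement reverses once t1 exceeds [p1/(p1 − p0 + p0/v0) − p1]/(1 − p1). For BCG this is 96.1% at v0 = 80% (t0 = 79.2%) and 98.2% at v0 = 90% (t0 = 89.6%). Tracing could rise, because Section 2.7.1 has maternity records taken to the EPI unit daily. It could fall, because some doses are still pending at end line. If t were halved, the BCG change would read 66.6 (v0 = 80%) or 64.6 (v0 = 90%).

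**End line window.** The timeline in Section 5.4 puts training in week 5 and final data collection in week 17, which leaves 12 intervention weeks. Births are assumed even over time, with a true gain of 46.
- One-year window: 12/52 = 23% intervention births, 30 × 0.231 = about 7 of 30 per facility. The gain reads 46 × 0.231 = 10.6.
- Study period, weeks 1–16: 4 of 16 weeks precede training, 30 × 4/16 = 7.5 of 30 births. The gain reads 46 × 12/16 = 34.5.

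**The case against.** The case against is substantial, and parts of it stand.

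- **The denominator is not written down.** The clause that incomplete records do not count belongs to the average-age sample. The maternity paragraph omits it and says such records help show how many children were not vaccinated there. Section 2.14 covers both indicators in one paragraph. It is right that the restriction is implied and not stated as a formula. But the quota, the shared method and Section 2.14 all point the same way, and no text tells the analyst to restore the incomplete records.
- **The tool points the other way.** Used at both rounds, it would largely remove the denominator bias. This stands. A reader might infer a demonstrated bias in a known direction, but the documents support only an unresolved conflict whose consequence depends on the reading.
- **The error may be small.** At v0 of 80–90% it is at most about 5 points with stable tracing. The sampling standard error of a change from 4% to 50% with 30 records per round is √(0.04 × 0.96/30 + 0.5 × 0.5/30) = 9.8 points per facility. Pooled over 450 records per round it is about 2.5 points, ignoring clustering. This limits the severity, although a systematic error does not shrink with pooling.
- **The one-year window needs collectors to follow the tool over Section 2.9.1.** Section 2.7.2 plans a refresher before end line. This stands as a mitigation, but the study-period window in Section 2.9.1 itself still includes pre-training births. A reader might also infer that births drawn from the wrong window are beyond repair. The documents do not support that: the tool records birth dates, and nothing bars sampling the registers again.
- **The study is descriptive and the exclusion is disclosed.** Both are true. What is not disclosed is the conflict between rounds and tool, or its effect on the change.

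**Conclusion.** The conflict is real and concerns the primary outcome. Followed literally, the baseline rule in Section 2.9.1 estimates p/v, while the end line wording and the tool admit a different denominator. On the stated assumptions, the gain is understated by 0.4–1.8 points if only baseline is restricted. It is overstated by about 2–5 points if both rounds are restricted and tracing is stable. It is largely free of denominator bias if the tool's rule is used twice. The error is larger if tracing is low or changes between rounds.

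Much larger distortions can be produced. With v0 = 40%, the BCG gain of 46 would read 40.0 (only baseline restricted) or 62.7 (both restricted, stable tracing). Nothing in the documents supports so low a traced share, so these are not expected results. The window problem can be larger than the denominator problem (10.6 or 34.5 against 46), but it depends on which text collectors follow and on even births.

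This should be fixed, but it does not invalidate the study, because births with missing dates are already recorded and the denominator can be recovered. Confidence is high that the texts conflict, and low on the direction and size of the bias.

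**What to change.** For the proportion indicator only:

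1. Drop the both-dates stopping rule. At both rounds take a systematic sample of 30 births per facility from the birth register. Keep every sampled birth with a birth date in the denominator, and count births with no dose recorded within 24 hours as not shown to be timely.
2. Set the baseline window to the previous 12 months. Set the end line window to births after that facility's training and up to 24 hours before extraction. Make Sections 2.4 and 2.9.1 and the delivery register tool agree on this.
3. Report the traced fraction for each round, with the traced-only proportion as a sensitivity analysis.
4. State the denominator in Section 2.11 and align Sections 2.9.1 and 2.14 and the delivery register tool. Keep the both-dates rule for the average-age indicator, where it is needed.

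The cost is wording. The tool already has the fields, including one for children not found. The drawback is that unmatched names and births vaccinated elsewhere count as not timely. The traced fraction makes that visible.

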2.1 Study Design

This is a three-part intervention study; baseline, implementation and final assessment. The purpose of this feasibility assessment is to report on the quantitative findings of an intervention integrating immunizations into maternity and newborn care across 15 health facilities in Cameroon. The overall aim is to assess the feasibility of administering OPV0 and BCG birth doses within 24 hours of birth in Cameroon:

- 1) Baseline data collection (4 weeks to complete)
- 2) *Intervention implementation* including health care worker training, and ongoing monitoring of the project (*12 weeks to complete*)
- 3) Final assessment to gather an end line estimate of the outcomes (4 weeks to complete)

The figure below is a graphic representation of the study outline.

Figure 1: Outline of pilot study

This pilot study is expected to take 20 weeks (see appendix 5.1 for a detailed project timeline) not including initial preparations such as obtaining ethics approval and training of data collectors. There is a possibility for delays due to an increase in COVID-19 pandemic. The study team will ensure the proper conduct of the study while respecting strict barrier measures.

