2.3 Study Period

The study is scheduled to take place for 20 weeks between January and April 2021.

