2.4 Study Population

The study population will include:

- All babies received in the maternity unit, or EPI unit for OPV0 and/or BCG vaccines in the 15 study facilities, during the 1-year baseline period and the intervention period;
- HCW from the 15 facilities involved in either EPI or maternity and newborn care

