2.5 Site selection criteria

The 15 health facilities will be selected based on the following inclusion and exclusion criteria while ensuring a mixture of semi-rural and urban, and large and small facilities, private and public facilities to observe feasibility and challenges across different levels of health care. Below are the proposed facilities purposefully selected through an iterative process with key stakeholders and EPI regional managers.

Table 2: Site selection criteria

Characteristics of health facilities selected	Urban setting	Semi-rural district
High volume (Above 100 average monthly deliveries)	Hôpital Nicolas Barre	HD Obala
(Above too average monthly deriveries)	HD Biyem Assi	
	HD Mifi	
	Hospital Protestant de Ngaoundéré	
Medium volume	Centre Medical Marie Reine Etoudi	CS Catholique Nkoabang
(50 – 100 average monthly deliveries)	HD Cite Verte	CMA de Mbe
		HD Foumbot
Low volume	CMA Ahala	CMA Dibi
(Below 50 average monthly deliveries)	CSI Catholique Baham	CS Deo Gracia, Nkolbisson
		CSI Urbain Mbalmayo 2

Inclusion criteria:

- Facilities providing maternity and newborn services including immunization services
- Facilities with either functional cold chain equipment with reliable power sources on site OR those located within one km of the district or another facility with cold chain equipment on site for easy access

Exclusion criteria:

- Facilities participating in research or interventions that will impact the outcomes measured
- Facilities experiencing higher than normal demand of COVID-19 patients will be excluded to not overburden HCWs further and potentially impact ongoing services
- Health facilities that participated in the 2019 birth platform assessment

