2.7 Training Sessions

2.7.1 Intervention training

Training sessions will be held at each of the 15 facilities separately, with the same study members leading the sessions. Rather than a central training, we will conduct training at each facility, thus reducing mass gatherings during the COVID-19 pandemic. Please see the infection control section (Section 3.2) for COVID-19 related processes during training. At each individual training, all relevant and available health staff, including EPI focal points and maternity and newborn staff, will be asked to participate. In facilities where not all staff are able to attend training, we will ensure at least 1 staff member per shift is able to attend, to enable the information to be passed down to all staff members. During the touch points with the facility, staff will assess if the information was indeed passed down. The sessions will be split into two half day to prevent the facility from closing for a day and to allow for staff to be properly distanced. Moreover, training sessions will be held outside where possible. Ahead of training, a member of the study team will discuss potential training dates with the facility in-charge, ensuring dates occur when most convenient for the staff. The principal investigator will ensure that participants are comfortable throughout training and data collection. The training session will incorporate the below components.

Table 4: Summary of components included in training session

Training Component	Details
Maternity and newborn clinical protocols	 Knowledge reinforcement for topics relating to birth dose immunizations including: Immunization basics (Note: the HCW participating in the study are anticipated to be well-versed in this already, however we can leverage modules from Vaccination in Practice training to provide targeted refreshers based on the audience) Birth dose vaccine information for OPV0 and BCG including safety information and contraindications

	 Immunization technique including vaccine handling and site of administration Directly address hesitancy surrounding opening a multi-dose vaccine vial for only 1 baby by sharing PEV policy on opening vials for one child as well as training on practices to carry this out effectively (e.g. updating wastage rates in forecasts for ordering, calculating shelf life once opened, etc.) Reinforce incorporating birth dose conversations into routine antenatal care visits and adding messaging into ANC talking points 		

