Roles and responsibilities of different providers	Outline detailed roles and responsibility for each HCW involved in birth dose vaccinations. Develop and train on facility-specific work flows (see section 2.5 above) which will orient HCW to how the birth dose administration fits into maternal and newborn care in terms of sequencing of services, process for recording and reporting and collecting the vaccines (see below), and mitigation plans and reminders (e.g. to follow safe newborn checklist and best practices in terms of handling emergencies first, etc.)		
Policy for birth dose administration	Provide information on updated policy for the birth dose vaccines to be administered in the maternity unit.		
Cold chain storage planning	During the baseline assessment, study members will assess each maternity unit's 24/7 access to a working refrigerator for vaccine storage. Each facility will have a plan (as part of the integrated workflow) on how to access the vaccines immediately after a birth takes place and will be outlined. For facilities without cold chain equipment, a daily schedule (including weekends and holidays) will be implemented where a morning trip is		
	made to the closest health facility or district health service with CCE to pick up vaccines and an evening trip is done to return unused vaccines to the same health facility.		
Recording and reporting harmonization	To ensure birth doses vaccines are properly recorded in both facility records and for the purposes of this pilot study, two record changes will take place and will be described in detail.		
	Birth dose maternity reporting form For the duration of the pilot study maternity units will be provided with a simple recording form with space to document each birth and information on birth doses given. Scenarios for accurately filling out the form will be discussed.		
	Updated birth registry		

	The birth registry will also be updated to include a column to check if the baby received the birth doses of BCG and OPV0 within 24 hours. At the end of each day, this paper will be brought to the EPI unit to incorporate into their record books. In addition, child health cards will need to be stored in maternity units so caregivers can acquire the book at the time of the birth dose administration, and the updated birth dose information is recorded on the health card.

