Out of facility births	We will use this opportunity to brainstorm strategies to address birth dose timeliness among out of facility births for future studies.

Contingency plan:

In the event of worsening COVID-19 pandemic, the pilot study will be restricted to facilities that have already completed training sessions and the intervention for the remaining facilities will be on hold until it is safe to continue with the intended pilot study.

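### The documents give three incompatible windows for the end line register samples; read literally, section 2.9.1 admits births from before training and understates the primary change

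*Combined protocol and SAP*

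**What the plan says.** All references are to the combined protocol and SAP.

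- **Section 2.9.1**, in the end line text for the immunization register and again for the maternity register: "The same sample size (N = 30) will be used with the sampling period being the duration of the study period".
- **Section 2.3**, headed Study Period: "The study is scheduled to take place for 20 weeks between January and April 2021". Section 2.1 builds the 20 weeks from three phases. The first is "Baseline data collection (4 weeks to complete"), followed by 12 weeks of implementation and 4 of final assessment.
- **Section 2.4** limits the babies studied to those seen "during the 1-year baseline period and the intervention period".
- **Section 5.3**: both register extraction tools have the collector count children entered in the year before the extraction date. No end line version is printed.
- **Section 5.4** puts facility training in week 5 and final collection of vaccine timing data in week 17.
- **Section 2.7.1**: training is held site by site, and "a member of the study team will discuss potential training dates with the facility in-charge". If COVID-19 worsens, "the pilot study will be restricted to facilities that have already completed training sessions" and the other sites wait.
- **Sections 2.10 and 2.11**: the primary outcome is the change in the proportion vaccinated within 24 hours, described by facility, baseline against end line.

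**The concern.** The end line sample should describe practice after integration. Under 2.9.1 as worded, births from the weeks before training are eligible for it, and the every-Xth-record interval is designed to spread the draw over the whole window. Each such birth pulls the end line proportion back toward baseline. Births just before the week 1-2 baseline extraction could also fall in both the baseline and the end line windows.

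The study is meant to inform HepB birth dose introduction, where the executive summary reports doubts about the feasibility of timely coverage. A diluted estimate could make a workable approach look weaker than it is. It would not create a false success.

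**Working it through.** **The plan's own figures.** 4 + 12 + 4 = 20 weeks, which agrees with 2.1 and the duration in 2.3. The calendar range in 2.3 does not hold it: January to April 2021 is 31 + 28 + 31 + 30 = 120 days, or 120/7 = 17.1 weeks.

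**Share of pre-training births in an even draw.** Extraction in week 17 leaves weeks 1-16 in the literal window.

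| Window | Pre-training weeks | Share f |
|---|---|---|
| 2.9.1 literal, weeks 1-16 | 4 | 4/16 = 25% |
| Same, week 5 counted as untrained | 5 | 5/16 = 31% |
| 2.9.1 literal, extraction at end of week 18 | 4 or 5 | 4/18 to 5/18 = 22-28% |
| 2.4, weeks 5-16 | 0 or 1 | 0/12 to 1/12 = 0-8% |
| One year back (tools unchanged) | 40 | 40/52 = 77% |

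**Effect on the change.** Assume that births are even over time, that pre-training births are at the baseline rate p0, and that the full effect p1 applies straight after training. Then observed change = (1 - f) x (p1 - p0). For the literal 2.9.1 window at week 17, 1 - f is 0.69 to 0.75. For the 2.4 window it is 0.92 to 1.00.

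**Count-back rule.** Section 2.9.1 has collectors start at the latest entry, take every Xth record and stop at 30 complete ones. Rounding of the interval is not stated. I took N = monthly births x 12/52 x 16, interval = N/30, births evenly spaced and all records complete. Site volumes were assumed: five sites in each Table 2 band, uniform over 8-49, 50-100 and 101-300 births a month.

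| Rounding | Pooled f, 4 weeks | Pooled f, 5 weeks |
|---|---|---|
| Down | 17.4% | 23.8% |
| Nearest | 21.8% | 28.2% |
| Up | 23% | 28.9% |

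So 1 - f runs from 0.711 to 0.826 pooled, or about 71-83% of the change.

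**Examples (assumed rates in the sampled records).**

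- From 4% to 50%, the true change is 46 points. It reads 46 x 0.711 = 32.7 to 46 x 0.826 = 38.0, a loss of 8-13 points.
- From 4% to 30%, the true change is 26 points. It reads 18.5 to 21.5, a loss of 4.5-7.5 points.

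**Against sampling error (95%, first example).**

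- One facility: 1.96 x sqrt((0.04 x 0.96 + 0.25)/30) = 19.2 points.
- Pooled, 450 v 450 records, diluted end line near 40%: 1.96 x sqrt((0.04 x 0.96 + 0.40 x 0.60)/450) = 4.9 points.
- Pooled, with an assumed ICC of 0.10: 4.9 x sqrt(1 + 29 x 0.10) = 9.6 points.

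**Spread between facilities (complete records, 4 pre-training weeks).** Rounded down, f is 0-23% at 8-49 births a month and 13-23% at 50-300. Rounded up, it is 17-27% and 20-27%. With 80% of records complete at random and the interval rounded down, the average is 19% below 50 births a month and 20% at 50 or more.

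**The case against.** The best reply is that this is loose wording with a clear intent. Section 2.4 names the intervention period, and 2.11 compares baseline with the end of the intervention. The plan also uses such phrases loosely elsewhere: "For the duration of the pilot study maternity units will be provided with a simple recording form", although that form is introduced at training. On that reading 92-100% of the change is seen. This stands as evidence of intent. It does not settle what is drawn, because collectors work from 2.9.1 and the printed tools. Section 2.7.2 plans a refresher before end line, which is an occasion to correct the window but does not state one.

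The analysis is also descriptive, has no success threshold, and is planned at facility level, where noise exceeds the bias. All true, and it lowers the severity. But a descriptive study rests on its point estimates, and more records would not remove this error. In the 4% to 30% example the pooled loss is smaller than the sampling error at an ICC of 0.10 (about +/-9 points).

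The error is recoverable too. Date of birth is extracted, so early births could be dropped later, and the newborn form gives a cross-check. But no analysis rule applies that exclusion, and dropping a quarter would leave about 30 x 0.75 = 22.5 records per site.

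A reader might infer that the dilution makes comparisons between facilities unfair. The documents do not support that as a general claim. The timeline trains every site in week 5. The wide 0-23% spread needs an interval rounded down, complete records and small sites, and it largely disappears if the interval is rounded up. A larger spread needs a training delay, which 2.7.1 allows but does not schedule. A reader might also infer that 2.9.1 is the collectors' only instruction, or that nothing limits the end line population. The tools also instruct them, and 2.4 does set a limit, although no sampling step carries it out.

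**Conclusion.** The point holds as a conflict between stated rules that bears on the primary outcome. Three windows are given, and two of them let pre-training births into the end line sample. Under the literal 2.9.1 window, 69-75% of the true change is seen with an even draw, or 71-83% pooled under count-back. The one-year wording would leave about 23% (1 - 0.77).

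These figures rest on even births, pre-training births at the baseline rate, an immediate full effect, the planned weeks 5 and 17 and, for the pooled range, assumed site volumes. The bias is toward no change. It matters mainly for pooled figures. The share may differ between facilities through rounding, incomplete records or delayed training, but the documents do not fix by how much. It should be corrected before end line extraction; it does not undermine the design.

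**What to change.** In 2.9.1, for both registers, replace the study-period wording with the intervention period of 2.4, counted from the date training is completed at each facility.

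- **24-hour indicator:** births from then until 24 hours before extraction.
- **Age indicator:** vaccinations given after that date.
- **Interval:** computed from the count in that window, with a stated rounding rule; take all births if there are fewer than 30.
- **Tools:** print end line versions of the two register tools with the same window.
- **Consistency:** reconcile 2.3 (including its calendar range), 2.4, 2.9.1 and 5.4.

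The cost is a wording change, two revised forms and one date per facility, which the study team has because it arranges and leads the training. There are two downsides. With 11-12 post-training weeks, sites below about 30/(12 x 12/52) = 10.8 to 30/(11 x 12/52) = 11.8 births a month will have fewer than 30 eligible births; this can affect only sites in the band "Below 50 average monthly deliveries". The age indicator will also still include some babies born before training.
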